**Effects of PSAPs on Speech Processing**

**NCT05076045**

**Study Protocol**

**March 14, 2022**

## **Background Information**

Hearing loss is the third most common chronic disability among Canadian seniors. Mild to moderate hearing loss in older adults is associated with communication deficits, including difficulty following a conversation in a noisy environment. It is also associated with accelerated cognitive decline and the early onset of dementia. In a recent study by our team ([name] et al., submitted), we showed that older adults who reported hearing problems had poorer executive functions than those who reported few hearing problems, suggesting a strong link between cognition and hearing.

Yet, despite its adverse effects on communication skills and cognition, mild to moderate hearing loss remains largely untreated, with only 20% of older adults with a hearing loss having access to hearing aids. In most Canadian provinces, Health Insurance covers only a portion of the cost of hearing aids, which can be thousands of dollars, making them unaffordable for many older adults.

A promising and much cheaper alternative is personal sound amplification products (PSAPs), electronic, portable, over-the-counter devices amplifying sound. They are analogues to drugstore reading glasses and do not require a prescription or hearing evaluation. PSAPs are becoming increasingly popular as millions of people in the United States use these devices to compensate for their hearing loss.

However, it remains an open question whether PSAPs can effectively reduce the adverse effects of hearing loss. As these devices gain popularity, there is an urgent need to objectively evaluate the impact of PSAPs on auditory processing and communication skills.

## **Research Question and Hypothesis**

This research investigates the immediate neurobiological and behavioural effects of PSAP use on speech-in-noise performance. The specific objectives are to:

- 1) Clarify whether using PSAPs is associated with improved speech perception in noise compared to an unaided condition in individuals with normal hearing or mild to moderate hearing loss.
- 2) Determine the role of listener characteristics, such as age, sex, education, self-reported hearing loss, objective hearing loss, and cognitive status, on performance during PSAPs use.
- 3) Study the neurobiological mechanisms of benefit using electroencephalography (EEG).

Our hypotheses are twofold:

- 1) We expect that wearing PSAPs for a single session will improve performance and lower self-reported listening effort during speech-in-noise perception.
- 2) We expect that the behavioural benefits of PSAPs will be associated with increased brain activity in auditory areas and increased functional connectivity between auditory and speech regions.

## Method

**Participants:** A total of 32 participants will be recruited. This sample size is similar to or larger than other studies examining the impact of PSAPs. Participants will be adults between the ages of 60 and 90 with normal hearing or mild to moderate hearing loss (no clinical diagnosis) who have never used hearing aids or any other type of hearing device.

Participants will be recruited through the Rotman Research Institute participant database. The selection of participants from the database will be based primarily on the hearing test results already available in the database. If necessary, additional participants will be recruited through advertisements.

Participation is voluntary and anonymous. All participants will sign a consent form before the start of the study and receive a modest stipend of \$15 per hour for their time. Reimbursement for parking fees or RTC tickets will also be provided.

### **Inclusion criteria:**

- Be between 60 and 90 years old.
- Normal hearing or mild to moderate hearing loss (i.e., hearing thresholds between 25 and 60 dB in both ears).

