### **Study Protocol:**

This study will consist of two sessions of three hours separated by one week apart. This study will include hearing evaluations, auditory and cognitive tasks, and various questionnaires assessing health, anxiety, depression, and listening ability.

In one session, participants will perform the auditory tasks without using any hearing devices, and in the other session, participants will be fitted, under laboratory supervision, with bilateral PSAPs. The order of the two sessions will be counterbalanced across participants so that some participants will complete the tasks with PSAPs in the first session and others in the second session. Counterbalancing will be generated by randomly assigning an order to each participant using the block randomization method (three blocks).

In each session, participants will perform the same tasks. Cognitive assessment and pure-tone audiometry will be conducted only in the first session.

In each session, the participant's brain activity during the speech perception tasks will be recorded by electroencephalography (EEG) using a 76-channel Active Two acquisition system (BioSemi V.O.F., Amsterdam, The Netherlands).

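### The inclusion criterion attaches a 25 to 60 dB range to normal hearing as well as to hearing loss; applied as written, its floor conflicts with the stated population and must be reconciled

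*Combined protocol and SAP*

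**What the plan says.** The Inclusion criteria contain two entries, age and hearing. The hearing entry reads "Normal hearing or mild to moderate hearing loss (i.e., hearing thresholds between 25 and 60 dB in both ears". It is the only place in the protocol that gives a dB limit for entry, and no section gives a separate numeric definition of normal hearing.

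The population is described in three other places, none of which has a dB limit:

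- Objective 1, under Research Question and Hypothesis, asks about PSAP use "compared to an unaided condition in individuals with normal hearing or mild to moderate hearing loss".
- The Participants paragraph under Method describes "adults between the ages of 60 and 90 with normal hearing or mild to moderate hearing loss (no clinical diagnosis".
- The Significance/Impact section extends the expected results to older adults with normal hearing as well as to those with mild to moderate loss.

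Objective 2 counts measured hearing among the listener characteristics to be studied: "self-reported hearing loss, objective hearing loss, and cognitive status, on performance during PSAPs use". On recruitment, Method states: "The selection of participants from the database will be based primarily on the hearing test results already available in the database".

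**The concern.** In the hearing criterion, the abbreviation i.e. and the dB range come after normal hearing and hearing loss have been joined into one phrase. Taken at face value, the range explains the whole phrase, and every participant needs thresholds of at least 25 dB in both ears. That is a floor on how well a participant may hear, in a study whose other sections say that people with normal hearing belong in it.

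Two things would be at stake if staff applied the line as written. The sample would lack the better-hearing listeners to whom objective 1 and the impact statement refer, so conclusions about them would have no data behind them. The hearing-loss predictor for objective 2 would also cover a shorter range, which makes any relation between hearing loss and PSAP benefit harder to estimate. Because candidates from the database are chosen mainly on existing hearing results, the wording of the hearing rule matters in practice.

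**Working it through.** The plan has no figure to reproduce on this point, so the check sets the statements side by side.

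**Step 1: direction of the scale.** The Hearing Tests section describes a pure-tone threshold as the lowest intensity that the listener perceives. A lower value therefore means better hearing, and a minimum of 25 dB removes the best hearers. No outside audiometric cut-off is needed for this.

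**Step 2: the two readings against the stated population.**

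| | Literal reading: range explains the whole phrase | Second reading: range explains only the hearing loss |
|---|---|---|
| Entry rule | 25 to 60 dB in both ears | No floor; no worse than 60 dB |
| Objective 1 (includes normal hearing) | Conflict | Agrees |
| Participants paragraph (includes normal hearing) | Conflict | Agrees |
| Significance/Impact (includes normal hearing) | Conflict | Agrees |
| Hearing range for objective 2 | Cut at 25 dB | Not cut at the lower end |
| Numeric definition of normal hearing | None | None stated; below 25 dB by implication |

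**Step 3: a test case.** Take a hypothetical listener at 15 dB at every frequency in both ears. Any average of those thresholds is 15 dB. Since 15 < 25, this person is out under the literal reading. Since 15 ≤ 60, the same person is in under the second. The result is the same whichever frequencies or average are used, so the contradiction does not depend on that missing detail.

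**Step 4: the minor gap, which frequencies.** The Hearing Tests section lists eight frequencies per ear, and the criterion does not say how the limit applies to them. Take a hypothetical ear at 20, 20, 20, 30, 45, 55, 65 and 70 dB from 250 to 8000 Hz:

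- Average of 500, 1000 and 2000 Hz: (20 + 20 + 30)/3 = 23.3 dB
- Average of 500, 1000, 2000 and 4000 Hz: (20 + 20 + 30 + 55)/4 = 31.25 dB
- Average of all eight: 325/8 = 40.6 dB
- Single thresholds above 60 dB: 65 and 70, so 2 of 8

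Under the second reading, this ear passes on all three averages and fails only if the ceiling applies to each frequency. Under the literal reading, it also fails on the three-frequency average, because 23.3 < 25.

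**Step 5: what is not affected.** Each participant is tested once with and once without PSAPs, so the comparison is made within the same person. An entry rule on hearing changes who is studied. It does not bias the difference between the two conditions in those who are studied.

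**The case against.** The strongest reply is that the second reading is the more natural one. The parenthesis directly follows the words for hearing loss. A literal floor would make the mention of normal hearing in the same line largely pointless, and the three other statements of the population all agree with the second reading. On this view the line is loosely punctuated and nothing more. Much of this stands: the intended meaning may well be the second reading, and the main comparison is safe either way. But an inclusion criterion is applied as worded, and this is the only one with numbers, so it should not depend on the reader inferring its scope.

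Some stronger inferences are tempting, and the documents do not support them:

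- *That normal-hearing adults will be excluded.* The protocol says that selection rests mainly on existing hearing results. It does not say that a 25 dB floor is applied to them.
- *That the loss for objective 2 can be quantified.* If thresholds were spread evenly up to 60 dB, with the same number of participants and the same residual SD, a floor at 25 dB would raise the standard error of a hearing-loss slope by 45/35 = 1.29 if the best listeners were otherwise at 15 dB, and by 60/35 = 1.71 if they were at 0 dB. The even spread and both starting values are assumptions. The Statistical Analyses section does not specify the regression either. These factors should carry no weight.
- *That eligibility must be confirmed again at the first session.* The protocol says "Cognitive assessment and pure-tone audiometry will be conducted only in the first session", but nowhere makes that audiometry an eligibility check. How people recruited by advertisement are screened for hearing is also not stated. That is missing detail and not part of this contradiction.

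**Conclusion.** The point holds as a contradiction in an operative inclusion rule. As written, the criterion sets a 25 dB floor that conflicts with objective 1, the Participants paragraph and the Significance/Impact section, and it would shorten the hearing range for objective 2. If the range was meant only for the hearing loss, the conflict disappears and so does the harm.

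Any consequence is limited to who is enrolled, to whom the results apply, and to the spread of one predictor. The number of listeners affected, out of the 32 planned, cannot be computed: the documents give no distribution of thresholds and do not say at what dB value normal hearing ends. The conclusion rests only on the wording of the criterion and on the protocol's own description of a threshold. The hypothetical ears illustrate the logic and are not evidence about the sample. The missing frequency or average is a small omission and does not carry the point.

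**What to change.** Make one of two changes, according to what the sponsor intends:

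1. If normal-hearing adults are to be included, reword the criterion so that 25 to 60 dB describes only mild to moderate hearing loss and 25 dB is not an entry floor. Entry then requires thresholds no worse than 60 dB in each ear.
2. If the floor is intended, remove normal hearing from the criterion itself, from objective 1, from the Participants paragraph and from the Significance/Impact section, and limit the conclusions accordingly.

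As a minor clarification in the same line, state which frequencies or which average the limit refers to. An average would admit listeners with single high-frequency thresholds above 60 dB. A per-frequency limit would admit fewer listeners with sloping losses.

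The first option costs the rewording of one line, and the second costs matching edits in four places. Neither needs a new test or changes the main analysis. When naming frequencies, the sponsor should check that they are among the results held in the recruitment database, because the protocol does not list those.

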### **Exclusion criteria:**

- Left-handed and ambidextrous (this is important to know given that handiness has been shown to influence speech perception);
- Mother tongue not English (this is also important because of differences in speech perception between monolingual and bilingual individuals);
- Language impairment (because this could be confounded with hearing impairment);
- Dementia (as it can affect the understanding of task instructions and the ease of fitting devices);
- Cerebrovascular diseases (as we study brain activity, and that can affect brain activity);
- Untreated vision impairment (as it can affect the reading of task instructions);
- Tinnitus and otologic disorders (as they can affect hearing);
- Cochlear implants and hearing aids (as these devices are used to treat hearing loss);
- Diagnosed addiction (alcohol or drugs) (as we study brain activity, and that can affect brain activity);
- Significant medical or neurocognitive conditions (other than MCI) or interventions likely to significantly impact cognitive function (e.g., epilepsy, stroke, traumatic brain injury with loss of consciousness > 5 minutes, brain tumour, multiple sclerosis, hepatitis C, developmental delay, electroconvulsive therapy) (as we study brain activity, and that can affect brain activity);

## Study protocol

- DSM-V diagnosis of major depressive disorder with active symptoms within 90 days of study entry, past or present psychosis, or other psychiatric disorders such as obsessive-compulsive disorder, generalized anxiety disorder, and bipolar disorder (as we study brain activity, and that can affect brain activity).

### **Study Protocol:**

This study will consist of two sessions of three hours separated by one week apart. This study will include hearing evaluations, auditory and cognitive tasks, and various questionnaires assessing health, anxiety, depression, and listening ability.

In one session, participants will perform the auditory tasks without using any hearing devices, and in the other session, participants will be fitted, under laboratory supervision, with bilateral PSAPs. The order of the two sessions will be counterbalanced across participants so that some participants will complete the tasks with PSAPs in the first session and others in the second session. Counterbalancing will be generated by randomly assigning an order to each participant using the block randomization method (three blocks).

In each session, participants will perform the same tasks. Cognitive assessment and pure-tone audiometry will be conducted only in the first session.

In each session, the participant's brain activity during the speech perception tasks will be recorded by electroencephalography (EEG) using a 76-channel Active Two acquisition system (BioSemi V.O.F., Amsterdam, The Netherlands).

### **Clinical Trial Registration:**

Theoretically, this study meets the definition of a clinical study since we plan to evaluate the effects of a device on health outcomes. However, participation in this study involves fewer obligations than formal clinical studies. Participants will only wear the devices for one three-hour session, and no medication is applied.

This clinical trial is registered here: <https://www.clinicaltrials.gov/ct2/show/NCT05076045/>.

### **EEG Acquisition:**

During each session, participants will be fitted with a cap containing 76 specially designed sensors to monitor brain activity using an electroencephalogram. Sensors will also be placed on the cheeks and forehead. To record a good brain activity signal, we will need to abrade (i.e., scrape) a bit of the scalp at each sensor location. Then, the gel will be inserted into each sensor. Brain activity will be recorded during the speech perception task. The preparation for the EEG is about 1 hour.

Participants may develop a headache or note some mild tenderness in the scalp area due to the placement of the brain-activity sensors. This occurs infrequently and is short-lasting.

**Telephone Interview Questionnaires (≈ 45 minutes):**

1. Demographic and Health Questionnaire: This questionnaire will document demographic and health information. Information on age, gender, education level, country of birth, race, ethnicity, language, and health will be documented. This questionnaire will be completed with the participant during a telephone interview to assess eligibility. The duration of this questionnaire is approximately 30 minutes.
2. The Edinburgh Handedness Inventory: This questionnaire is a measurement scale used to assess the dominance of a person's right or left hand in everyday activities. This questionnaire will be completed with the participant during a telephone interview to determine eligibility. The duration of this questionnaire is approximately 5 minutes.

**In-person Questionnaires (≈ 20 minutes):**

3. Speech, Spatial and Qualities of Hearing Scale (SSQ): This questionnaire measures self-perception of hearing. It consists of 49 questions divided into three sections documenting hearing abilities in different daily life situations. The questionnaire includes 14 questions on speech-related hearing disabilities, 17 questions on spatial-related hearing disabilities and 18 questions on other hearing disabilities. For each question, participants will be asked to indicate on a scale of 0 to 10 if they would be completely unable (score of 0) or perfectly able (score of 10) to perform what is described in the question (e.g., understand speech in noise). The duration of this questionnaire is approximately 10 minutes.
4. The 15-item Geriatric Depression Scale (GDS): This questionnaire is designed to detect symptoms of depression but is not used for diagnostic purposes. It consists of 15 yes/no questions about mood, aspirations, and daily activities. The duration of this questionnaire is approximately 5 minutes.
5. The 10-item Geriatric Anxiety Scale (GAS): This questionnaire is designed to detect anxiety symptoms but is not used for diagnostic purposes. It consists of 10 questions that are answered with "Not at all," "Sometimes," "Most of the time," and "All of the time." The questions also concern mood, aspirations, and daily activities, focusing on anxiety. The duration of this questionnaire is approximately 5 minutes.

**Cognitive Assessment (≈ 20 minutes):**

1. Montreal Cognitive Assessment: General cognitive functioning will be assessed using the Montreal Cognitive Assessment Hearing Impaired (MoCA-HI), a 10-minute cognitive tool. This assessment measures several cognitive domains, including orientation, memory, visuospatial function, executive function, and language.

**Hearing Tests (≈ 15 minutes):**

1. Pure tone Audiometry: Pure tone audiometry will measure hearing. During this test, pure tones are sent through headphones into one ear and then into the other. This allows us to

## Study protocol

determine the lowest intensity at which the sounds are perceived. Pure tone thresholds will be measured separately for both ears at the following frequencies: 250, 500, 1000, 2000, 3000, 4000, 6000, and 8000 Hz. This test will take about 10 minutes.

2. Quick Speech in Noise (QuickSIN) test: The QuickSIN test estimates speech-in-noise ability. Four sentences with five keywords per sentence are presented in four-talker babble noise. The sentences are presented at pre-recorded SNR ratios which decrease in 5-dB steps from 25 (very easy) to 0 (very difficult). The duration of this task is approximately 5 minutes.

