### **Statistical Analyses:**

The outcome of the QuickSIN is the signal-to-noise ratio (SNR) loss. Analyses will depend on the normality of the scores. Normal: Paired-sample t-test; non-normal: Wilcoxon signed rank test.

The outcome measures for the syllable discrimination paradigm are reaction time and accuracy. We will use linear mixed-effects (LME) models separately for each dependent variable. Models will include Session (without, with) and SNR as within-subject factors. For self-reported listening effort, the listening effort score will be analyzed using a cumulative link mixed model.

Regression models with health and demographic factors will be conducted to identify predictors of the benefits.

Brain activity will be recorded using EEG. EEG recordings will be processed offline using Brain Electrical Source Analysis software (BESA 7.1). Measures of sensory-evoked response, event-related potential and connectivity will be analyzed using BESA Statistics.

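### Four QuickSIN sentences for six signal-to-noise levels: does the plan need to change?

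*Combined protocol and SAP*

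**What the plan says.** Under Hearing Tests, the second item describes the QuickSIN: "Four sentences with five keywords per sentence are presented in four-talker babble noise". It continues: "The sentences are presented at pre-recorded SNR ratios which decrease in 5-dB steps from 25 (very easy) to 0 (very difficult". On length it says: "The duration of this task is approximately 5 minutes". It gives no number of sentences per level or per session.

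The section headed Study Protocol covers the two visits: "In each session, participants will perform the same tasks". The exception is stated next: "Cognitive assessment and pure-tone audiometry will be conducted only in the first session". The QuickSIN is not in that exception, so it is given at both visits, one week apart, once with the devices and once without. The order of the two conditions is randomised in blocks so that it is counterbalanced across participants.

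Statistical Analyses names the endpoint, "The outcome of the QuickSIN is the signal-to-noise ratio (SNR) loss", and the comparison: "Normal: Paired-sample t-test; non-normal: Wilcoxon signed rank test". It does not give the rule that turns keywords into SNR loss, and no section says whether the second visit uses the same sentences as the first.

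**The concern.** Read literally, the description contradicts itself. Four sentences cannot be spread over a range of six levels, so a reader cannot tell whether a participant's score at one visit rests on 20, 30 or 120 keywords. The precision of the score depends on that number. SNR loss is the first outcome named in Statistical Analyses, and it bears directly on the first objective, whether the devices improve speech perception in noise.

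Two silences add to the worry. The scoring rule is not written out. The test is also repeated after a week with no word on whether the sentences are new. If they were the same, participants might remember some of them, and a paired test without an order term would leave that practice gain in the differences.

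**Working it through.** **Inputs.** From Hearing Tests: 4 sentences, 5 keywords per sentence, SNRs from 25 to 0 dB in 5-dB steps, about 5 minutes (300 s). From Participants: 32 people. From Study Protocol: randomised order in three blocks. The order split, practice gain and standard deviations used below are assumptions, because the documents give none.

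**Step 1: count the levels.** (25 − 0)/5 + 1 = 6, namely 25, 20, 15, 10, 5 and 0 dB. Four sentences over six levels is 4/6 = 0.67 per level. The stated four therefore cannot be reconciled with the stated range if it is the total.

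**Step 2: compare the readings with the stated duration.**

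| Reading | Sentences | Keywords | Seconds per sentence |
|---|---|---|---|
| Four in all | 4 | 4 × 5 = 20 | 300/4 = 75 |
| One per level | 6 | 6 × 5 = 30 | 300/6 = 50 |
| Four per level | 4 × 6 = 24 | 24 × 5 = 120 | 300/24 = 12.5 |

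Four per level keeps the word *four*, covers all six levels and gives the most natural pace. One per level contradicts the word *four*. The timing is only a pointer, since the 5 minutes may include instructions, responses and scoring.

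**Step 3: trace what depends on the number.** Nothing in the plan is calculated from it. The sample size is justified by comparison with other studies of these devices, not by a standard deviation of SNR loss. The paired t-test or Wilcoxon test takes one score per person per condition, whichever reading is right. If sentence errors are independent (assumption), scoring error shrinks with the square root of the number of sentences, so 24 sentences have half the error of 6: √(6/24) = 0.5. If the same number is given at both visits, that error is already contained in the observed within-person differences. The test then stays valid and its interval shows the precision actually achieved.

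**Step 4: test the reuse scenario.** Suppose the same sentences were used twice and improved second-visit scores by g dB. Let the true device benefit be d, expressed as improvement. The aided-minus-unaided difference is d + g for people who use the devices second and d − g for those who use them first. The mean is d + m·g, where m is the difference between the two order counts divided by 32.

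- 16/16 split: m = 0, so there is no shift.
- 17/15 split: m = 2/32 = 0.0625, so a 1 dB gain shifts the mean by 0.06 dB.

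A small imbalance is plausible because 32/3 = 10.67, so the three blocks cannot all be the same size.

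**The case for a change.** The strongest case for a change is that an outcome central to the first objective should have its test length, scoring and sentence material stated in the plan. Counterbalancing protects the mean but not the spread. In the reuse scenario the standard deviation of the differences becomes √(SD² + g²(1 − m²)). With an assumed SD of 2 dB, gains of 0.5, 1 and 1.5 dB give 2.06, 2.24 and 2.50, so the confidence interval is 3%, 12% and 25% wider. For a 1 dB gain, the widening runs from 8% to 20% as the assumed SD runs from 2.5 down to 1.5.

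The algebra is right, and it is fair to want the number of sentences per level and per visit on record, along with whether any are repeated. A written report of the study should give them.

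The rest does not carry a change. The widening requires sentence reuse, which no section states, and its size is set entirely by a chosen gain and SD. It is a loss of precision, not a bias. Familiarity with the task could also produce a gain with fresh sentences, so the absence of an order term is a separate question from the sentence count. Prescribing sets of sentences balanced over device and order would add a design requirement to cure a fault that the documents do not show. Nor is it fair to say that the test could not be repeated by others: the protocol names a specific test with fixed recorded levels and names its score.

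**Conclusion.** The mismatch is real: four sentences are stated against six levels. It is best read as a dropped qualifier in one sentence, and it affects no calculation, sample size or decision rule in the plan. Leaving out the scoring formula of a named test is an ordinary economy in a short protocol. Silence on the sentence material is a gap that the staff giving the test can be expected to fill sensibly. Even if they reused sentences, the mean difference would move by nothing under an equal split, or by about 6% of the practice gain under a 17/15 split.

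No change follows. This rests on the same number of sentences being given at both visits, which is how the requirement that the tasks be the same is naturally read, and on the order being close to balanced, as the block randomisation intends. The preference for 24 sentences is an inference from the wording and the stated duration, and the verdict does not depend on it.
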